## 5.2 Exclusion Criteria

- 5.2.1 Patient has had chemotherapy or radiotherapy within 2 weeks (6 weeks for nitrosoureas, anti-angiogenic agents, or mitomycin C) prior to entering the study or those who have not recovered from adverse events due to agents administered more than 4 weeks earlier.
- 5.2.2 Patient receiving any other investigational agents.
- 5.2.3 Patient who has had any prior radiotherapy to the treatment site(s). As in, definitive therapy for lesion of interest. Field overlap from previous treatment is permitted at the discretion of the treating investigator.
- 5.2.4 Patient is taking concurrent drugs that are contraindicated with Nelfinavir, including any of the following:
  - Alfuzosin
  - Cisapride
  - Sildenafil (Revatio®)
  - Amiodarone
  - Quinidine
  - Rifampin
  - Dihydroergotamine

Ergonovine  
Ergotamine  
Methylergonovine  
Hypericum perforatum (St. John's wort)  
Lovastatin  
Simvastatin  
Pimozide  
Midazolam  
Triazolam  
Oral Midazolam

- 5.2.5 Patient refuses to take a pregnancy test prior to treatment if the patient is a woman with child bearing potential.
- 5.2.6 Patient is participating in a concurrent treatment protocol.
- 5.2.7 Patient is a pregnant woman (pregnant women are excluded from this study because radiation treatment has known potential for teratogenic or abortifacient effects).
- 5.2.8 Patient refusesto sign informed consent.
- 5.2.9 Patient has poor liver function (>2.5 times normal of ALT/AST/Alk phos) suggestive of cirrhosis or steatohepatitis.
- 5.2.10 Patient has been treated with Nelfinavir within 3 months of entry into this trial.
- 5.2.11 Patient is receieving Warfarin (Coumadin).

## 6. TREATMENT PLAN

### 6.1 Diagnostic Procedures

A CT scan or MRI will be performed for tumor localization using rigid immobilization appropriate for stereotactic treatment. A separate PET-CT may be performed (all are optional) for diagnostic purposes and can be used for treatment planning with fusion -- this study would be done identically if the patient were having standard moderate dose radiation.

### 6.2 Therapeutic Procedures

Upon confirmation of eligibility and enrollment in the study, the following will be completed:

- 1) Demographics review, medical history and clinical exam
- 2) Review of concurrent medications
- 3) Vital signs, height and weight
- 4) CBC, chemistry panel and coagulation profile

- 5) Peripheral blood mononuclear cells will be collected and subsequently assayed for phospho-Akt before administration of Nelfinavir, on the day of SBRT, and optionally at the 1MFU.
- 6) CT or MRI of the involved site(s) (if not previously conducted within 1 month of start of Nelfinavir).
- 7) Positron Emission Tomography scan (optional) (if not previously conducted within 1 month of start of Nelfinavir).

Upon entry into the protocol, all patients will be seen by at least one of the Co-Investigator Radiation Oncologists. CT simulation will be performed with fabrication of a radiation therapy immobilization device (such as the Alpha Cradle) which will be custom made for each patient. The treating radiation oncologist will identify the location of the tumor. Gross tumor volume (GTV) delineation will be performed with a diagnostic radiologist on sequential axial computed tomography images. A radiosurgical treatment plan will be developed based on tumor geometry and location. The dose will be prescribed to the minimal isodose line that completely covers the GTV plus a 5 mm margin. Adjacent normal structures including but not limited to the heart, esophagus, aorta, spinal cord, kidneys, rectum, bowel, liver, and stomach within 5 cm of the GTV will be identified for the purpose of limiting incidental radiation to these structures.

In addition, prior to treatment delivery, a four-dimensional cone beam CT study will be performed on individual patients to assess respiration in these patients and to determine tumor targeting accuracy for those tumors that may be subject to respiratory motion such as those in the lung or liver. If tumor motion is greater than 5 mm, the planning target volume (PTV) will be expanded to account for respiration.

Within three weeks of the initial treatment planning imaging study, SBRT will be administered using image-guidance. An Alpha Cradle (or equivalent immobilization device) will be used to minimize movement of the chest, spine, and abdomen during treatment. During treatment, real time cone beam CT images of the patient's body site of interest will be obtained. Cone beam CT scan will be obtained immediately prior to treatment and will be repeated until the treatment shift, required to align the CT planning scan and the cone beam CT scan performed on the day of treatment cone beam CT, is within tolerance for the body site.

The patient will begin on 1250 mg oral Nelfinavir twice a day for seven days prior to starting SBRT. Once having completed the Nelfinavir, the patient will begin SBRT. Afterwards, the patient will again take Nelfinavir for 7 days. If scheduling or safety prevents all lesions from being irradiated within one day, participants will complete Cycle #2 of Nelfinavir then undergo a minimum of 7 days "clear out". Following this break participants will repeat Cycle #1 of Nelfinavir then receive radiation to the remaining lesions followed by a repeat Cycle #2 of Nelfinavir. This process may not exceed three "rounds" of treatment (NFV1, SBRT, NFV2) and may include repeat imaging and/or blood work.. This dose of Nelfinavir has been shown to reliably inhibit Akt phosphorylation.

Patients will be evaluated for adverse events/toxicities during their treatment.

6.2.1 The dose limits for surrounding critical structures are as follows:

- **Spinal Cord:** maximal allowable dose should be = 1000 cGy in 1 fraction
- **Lung:** 2/3 of the lung volume should be kept under 500 cGy.
- **Heart:** 50 % of the heart volume should be kept under 1000 cGy.
- **Esophagus:** 50 % of the esophagus volume should be kept under 1000 cGy and no single point dose in the esophagus should exceed 2000 cGy.
- **Brachial Plexus:** maximal allowable point dose = 1000 cGy
- **Liver:** One third of the uninvolved liver or approximately 700 cc <15 Gy.
- **Kidneys:** 75% of volume of each kidney <5 Gy.
- **Small Bowel:** <5% of bowel limited to <20 Gy.

### 6.3 Follow-Up Procedures

Subsequent to SBRT, patients will be followed clinically for toxicity and interval history at Months 1, 2, 3, 6, 12, and every 6 months thereafter until 3 years post SBRT. A detailed medical and physical examination will be performed at 4 weeks, 3 months, 6 months and 1 year post SBRT. The following procedures are optional at Months 1, 3, 6 and every 6 months through 3 years post SBRT:

- A complete blood count (CBC) and comprehensive chemistry panel
- CT scan or MRI including the treated site (Note: this is required at Months 3 and 6 for the reason noted below)
- Physical Exam and ECOG Performance Status

PET-CT will be recommended at 3 months, 6 months, and annually thereafter however all are optional.

CT scans at 3 and 6 months will be used to determine radiographic response based on RECIST 1.1 criteria.

All follow-ups may be conducted by telephone for patient convenience. Study staff will request any of the optional procedures noted above that were performed by local physicians to be forwarded for study records.

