Based on data above, in this study we will evaluate whether a Nelfinavir plus a single fraction of SBRT can be combined with Nelfinavir to control liver metastases with up to 5 liver metastases. Patients will be closely monitored for grade 3 or above liver toxicity including RILD.

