e. Serum pregnancy test (women of childbearing potential).  
f. Should occur within 30 days of start of Nelfinavir.

SBRT and Nelfinavir

Protocol Chair: [name]

J12137 (NA\_00069585) - May 19, 2020

g. Follow up AE evaluations may be conducted via phone.
h. Required at 3 and 6 months
i. May be conducted via telephone. All procedures are optional, EXCEPT for interval history and AE evaluations. Study staff will remind subjects of upcoming optional procedures at each telephone or follow-up visit. If obtained locally, staff will request that the results be forwarded for study records.

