## 12.5 Nelfinavir

12.5.1 The safety of VIRACEPT (Nelfinavir mesylate) was studied in over 5000 patients who received drug either alone or in combination with nucleoside analogues. The majority of adverse events were of mild intensity. The most frequently reported adverse event among patients receiving VIRACEPT was diarrhea, which was generally of mild to moderate intensity. The frequency of Nelfinavir-associated diarrhea may be increased in patients receiving the 625 mg tablet because of the increased bioavailability of this formulation.

Adverse events occurring in patients receiving VIRACEPT in all phase II/III clinical trials and considered at least possibly related or of unknown relationship to treatment and of at least moderate severity are listed below:

*Body as a Whole:* abdominal pain, accidental injury, allergic reaction, asthenia, back pain, fever, headache, malaise, pain, and redistribution/accumulation of body fat.

*Digestive System:* anorexia, nausea dyspepsia, epigastric pain, gastrointestinal bleeding, hepatitis, mouth ulceration, pancreatitis and vomiting.

*Hemic/Lymphatic System:* anemia, neutropenia, leukopenia and thrombocytopenia.

*Metabolic/Nutritional System:* increases in alkaline phosphatase, amylase, creatinine, phosphokinase, lactic dehydrogenase, SGOT, SGPT and gamma glutamyl transpeptidase; hyperlipemia, hyperuricemia, hyperglycemia, hypoglycemia, new onset or exacerbation of diabetes mellitus, dehydration, hepatitis, jaundice, and liver function tests abnormal.

*Musculoskeletal System:* arthralgia, arthritis, cramps, myalgia, myasthenia and myopathy.

*Nervous System:* anxiety, depression, dizziness, emotional lability, hyperkinesia, insomnia, migraine, paresthesia, seizures, sleep disorder, somnolence and suicide ideation.

*Respiratory System:* dyspnea, pharyngitis, rhinitis, and sinusitis.

*Skin/Appendages:* dermatitis, folliculitis, fungal dermatitis, maculopapular rash, pruritus, sweating, and urticaria.

*Special Senses:* acute iritis and eye disorder.

*Urogenital System:* kidney calculus, sexual dysfunction and urine abnormality.

12.5.2 The following additional adverse experiences have been reported from post marketing surveillance as at least possibly related or of unknown relationship to VIRACEPT:

*Body as a Whole:* hypersensitivity reactions (including bronchospasm, moderate to severe rash, fever and edema).

*Cardiovascular System:* QTc prolongation, torsades de pointes.

*Digestive System:* jaundice.

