### 15.4 Early Stopping Guidelines:

This study will monitor site-specific grade 4/5 toxicity. If it becomes evident that the proportion of grade 4/5 toxicity at specific sites convincingly exceeds 20%, the study will be halted for a safety consultation. Specifically, we will apply a Bayesian toxicity monitoring rule that suspends the enrollment if the posterior probability of toxicity being larger than 20% threshold is 75% or higher. The monitoring rule uses Beta (0.5, 5.5) as prior distribution. This means that our prior guess of the proportion of toxicity is 8.3%, and there is 90% chance that this proportion is 0.04%-30.6%. The monitoring will start from the 7th patient, and the decision rule for safety stopping is as follows:

Stop if:

# grade 4/5 toxicities $\geq$	4	5	6	7	8	9	10
Out of # patients	7 - 10	11 - 14	15 - 18	19 - 23	24 - 27	28 - 32	33 - 36
# grade 4/5 toxicities $\geq$	11	12					
Out of # patients	37 - 41	42					

The operating characteristics of the stopping rule are shown below and are based on 5000 simulations:

True AE rate	% simulated trials declaring unsafe	Average sample size (out of 42)
0.10	2.1	41.4
0.15	11.3	39.2
0.2	32.7	34.3
0.25	59.5	27.7
0.3	81.9	21.2
0.35	93.6	16.1
0.4	98.3	12.7

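### The plan contradicts itself on whether any laboratory safety test after baseline is compulsory, so the promised liver monitoring and three safety rules may have no scheduled laboratory input

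*Combined protocol and SAP*

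**What the plan says.** The commitment is in section 4.6: "Patients will be closely monitored for grade 3 or above liver toxicity including RILD". Section 12.5 lists hepatitis, raised transaminases and abnormal liver function tests among the effects of nelfinavir, and, for blood, "anemia, neutropenia, leukopenia and thrombocytopenia".

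At entry, section 6.2 requires "CBC, chemistry panel and coagulation profile", and the calendar places these no more than 30 days before nelfinavir (footnote f). The calendar then leaves the blood count and chemistry rows empty in the Cycle #1, SBRT and Cycle #2 columns and marks them next at 1M, with neither the optional asterisk nor footnote i.

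Section 6.3 differs: "The following procedures are optional at Months 1, 3, 6 and every 6 months through 3 years post SBRT". The list that follows includes the blood count, the chemistry panel, and physical examination with performance status. It adds: "All follow-ups may be conducted by telephone for patient convenience". From the 3M column on, calendar footnote i says: "All procedures are optional, EXCEPT for interval history and AE evaluations". In repeat treatment rounds, blood work is permitted but not required (6.2, 6.4 and the calendar).

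On physical examination, 6.3 also says: "A detailed medical and physical examination will be performed at 4 weeks, 3 months, 6 months and 1 year post SBRT".

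Three rules act on toxicity. The removal criterion (6.6) covers grade IV or worse events on nelfinavir before SBRT. The run-in (15.3) counts related grade 3 or higher events in the first six patients over 30 days. For the stopping rule, 15.4 says: "This study will monitor site-specific grade 4/5 toxicity".

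**The concern.** Liver enzyme rises and low blood counts can be silent, and a telephone call does not find them. If nobody has to draw blood, such an event is recorded as no event. Undetected events can only lower the counts that feed the three rules, so any error runs one way, towards a safer-looking regimen. The toxicity objective in 3.2 is affected in the same way.

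The setting gives this some weight. Section 15.3 says there is no earlier experience with the combination in this population. Section 5.1.8 admits patients with platelets from 50,000/µL and neutrophils from 1,000/µL, and 5.2.9 excludes liver enzymes only above 2.5 times normal. A site also cannot tell from the text whether a missing 1-month panel is a deviation.

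**Working it through.** **1. The schedule, place by place (blood count and chemistry)**

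| Time | Calendar | Section 6.3 | Footnote i |
|---|---|---|---|
| Baseline | marked | not covered (6.2 requires it) | not attached |
| Cycle #1, SBRT, Cycle #2 | not marked | not covered | not attached |
| 1M (±5 days) | marked, no optional flag | optional, telephone allowed | not attached |
| 3M to 36M | marked | optional, telephone allowed | attached: optional |
| Repeat rounds | permitted only | not covered | not attached |

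The direct conflict is at 1M. The calendar also marks vital signs, height and weight there, which suggests a visit in person. The optional list in 6.3 carries an explicit exception for imaging, which is required at Months 3 and 6. It has no such exception for the laboratory panels.

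**2. Scheduled laboratory input to each rule**

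| Rule | If 6.3 governs | If the calendar governs |
|---|---|---|
| Removal (6.6) | none | none |
| Run-in (15.3) | none | the 1M sample, if it falls by day 30 |
| Stopping rule (15.4) | none | the 1M sample; later ones optional |

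**3. Sampling gap if the calendar governs** (one month taken as 30 days)

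- One round: nelfinavir starts on day 0, SBRT is on day 7, Cycle #2 runs from day 8 to day 14, and 1M is day 7 + 30 = 37. The baseline sample can be 30 days before day 0, so the gap is up to 30 + 37 = 67 days, or 72 at the end of the visit window. The 1M sample comes 37 − 14 = 23 days after the last nelfinavir day.
- Three rounds at minimum spacing: SBRT falls on days 7, 29 and 51 (each further round adds 7 + 7 + 7 + 1 = 22 days). Follow-up runs from SBRT completion, so the gap is up to 30 + 51 + 30 = 111 days.
- Run-in window: 1M spans days 25 to 35 after SBRT and the window closes at day 30, so even a compulsory 1M sample can come too late.

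**4. Which events can be missed**

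Under 12.2.1 a laboratory abnormality is an adverse event only if it causes signs or symptoms, or needs treatment or further tests. Symptomatic events are sought at the compulsory evaluations: end of Cycle #1 or the SBRT day, end of Cycle #2, 1M, 2M, 3M and later. A silent abnormality needing no action would not count even if measured. What remains is the silent abnormality that would have led to treatment or work-up had it been seen.

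**5. Can the effect be sized?**

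The plan's own figures reproduce. With posterior Beta(0.5 + x, 5.5 + n − x) and the 75% criterion, every boundary from n = 7 to 42 matches 15.4. An exact binomial recursion gives stopping probabilities of 2.2, 11.6, 32.5, 59.4, 81.4, 93.6 and 98.4% at true rates 0.10 to 0.40. The printed simulations give 2.1, 11.3, 32.7, 59.5, 81.9, 93.6 and 98.3%.

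Under-detection needs a detection fraction d, with observed rate = d × true rate. The documents give no d, so the following is an illustration by assumption only. The run-in rows use P(3 or more of 6) and treat events as at most one per patient.

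| Rule, true rate | d = 1 | d = 0.75 | d = 0.5 |
|---|---|---|---|
| Stopping, 0.10 | 2.2% | 0.7% | 0.1% |
| Stopping, 0.20 | 32.5% | 11.6% | 2.2% |
| Stopping, 0.30 | 81.4% | 45.9% | 11.6% |
| Run-in, 0.20 | 9.9% | 4.7% | 1.6% |
| Run-in, 0.40 | 45.6% | 25.6% | 9.9% |

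The table shows that the printed operating characteristics presume full detection. It does not estimate the loss in this trial.

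**The case against.** Much of the opposing case stands. The definition in 12.2.1 removes silent findings that need no action, and the compulsory evaluations cover symptomatic toxicity, so the affected class is narrow. Grade 5 events are deaths and cannot be laboratory-only. Section 12.5 describes most nelfinavir events as mild, and the prior in 15.4 centres on 8.3%. At a true rate of 10% the stopping probability is only about 2%, so missed events could lower it by at most about 2 points. Other safeguards exist: the liver exclusion in 5.2.9, the liver dose limit in 6.2.1 and committee oversight in section 13. Toxicity is a secondary objective, and the primary analysis of local progression is untouched.

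A reader might infer that a site can follow the whole plan and never draw a safety sample after baseline. That holds only if 6.3 overrides the calendar, which no text says. A reader might also infer that the chance of halting at a true 30% rate falls from 81.9% to 32.7% or 11.3%. Those values need one third or one half of grade 4/5 events to be missed, and nothing in the documents supports either fraction.

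The objection does not remove the contradiction at 1M, the empty treatment columns set against the promise in 4.6, or the conflict over physical examination.

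**Conclusion.** The point holds as a contradiction that leaves safety ascertainment undefined. If 6.3 governs, no laboratory test after baseline is compulsory, and none of the three rules has scheduled laboratory input. If the calendar governs, one panel at 1M is required. It can fall after the run-in window closes, it comes about three weeks after the last nelfinavir dose, and 6.6 still has no scheduled laboratory input.

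The direction of bias is clear: towards safe, and confined to silent abnormalities that would have needed treatment or work-up. Its size cannot be computed from the documents. The gaps of up to about 67 days (one round) and 111 days (three rounds) rest on a 30-day month, the earliest permitted baseline and minimum spacing between rounds. Separately, 6.3 both requires and makes optional a physical examination at the same visits.

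This should be fixed. It does not threaten the primary analysis.

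**What to change.** - Reconcile 4.6, 6.3, the calendar and footnote i. State that the blood count and chemistry panels already marked in the calendar, at least at 1M, are compulsory with a local laboratory allowed, and take them off the optional list in 6.3. If any 3M or later panel is to be compulsory, exempt it from footnote i.
- Have the sponsor reconcile the timing of laboratory assessment with the 30-day run-in window (15.3) and the on-nelfinavir period in 6.6, and state what applies in repeat rounds. No sampling schedule is proposed here. Adding tubes to the existing phospho-Akt draw on the SBRT day would not by itself settle 6.6, because Cycle #1 ends the day before.
- Reconcile the two statements on physical examination in 6.3, together with footnote i.

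The cost is one protocol amendment to 6.3 and the calendar. The 1M panels are already listed, so no new test is created there. The downside is that patients followed by telephone need a local laboratory visit.

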### 6.4 Duration of Therapy

The patient will initiate Nelfinavir oral therapy twice daily seven days prior to SBRT. Within three weeks of the initial treatment planning imaging study, SBRT will be administered in a single dose to each treated lesion. After completion of SBRT a second seven day cycle of Nelfinavir will occur.

If scheduling or safety prevents all lesions from being irradiated within one day, participants will complete Cycle #2 of Nelfinavir then undergo a minimum of 7 days “clear out”. Following this break participants will repeat Cycle #1 of Nelfinavir then receive radiation to the remaining lesions followed by a repeat Cycle #2 of Nelfinavir. This process

may not exceed three “rounds” of treatment (NFV1, SBRT, NFV2) and may include repeat imaging and/or blood work..

### **6.5 Duration of Follow-Up**

It is anticipated that this study will last 3 years.

### **6.6 Criteria for Patient Removal**

Unacceptable adverse events grade IV or greater with an attribution of possibly related while on Nelfinavir before SBRT.

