### **7.3 Agent Accountability**

Only subjects enrolled in the study may receive Nelfinavir, in accordance with all applicable regulatory requirements. Subjects enrolled on the study will self-administer nelfinavir and keep track of their dosing intake via a study drug administration record. Nelfinavir will only be dispensed to the patient when the treating physician involved in the study provided a written order.

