## **8. DOSING DELAYS/DOSE MODIFICATIONS**

There will be no dose modifications.

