### 10. STUDY CALENDAR

Parameter	Pre-Study	NFV^ Cycle #1	SBRT ~	NFV^ Cycle #2	Follow-Up%								
					1M (+/- 5 days)	2M (+/- 7 days)	3M i (+/- 7 days)	6M @, h, i	12M @,i	18M @,i	24M @,i	30M @,i	36M @,i
Informed Consent	X												
Demographics	X												
Med HX & Medication Rev	X				X		X	X	X	X	X	X	X
Physical Exam	X				X		X	X	X	X	X	X	X
Vital Signs	X				X								
Height	X				X								
Weight	X				X								
Perf Status	X		X		X	X	X	X	X	X	X	X	X
CBC w/ Diff a	X f				X		X	X	X	X	X	X	X
Serum Chem b	X f				X		X	X	X	X	X	X	X
Coagulation Profile	X f												
Blood Draw for Phospho-Akt	X f		X		X*								
CT or MRI h (of Involved Site(s) o )	X f				X		X	X	X	X	X	X	X
PET-CT*	X f						X	X		X		X	
CT-Guided Fiducial Placement*	X												
AE Evaluation g	X	X d		X d	X	X	X	X	X	X	X	X	X
B-HCG e	X												

^ Nelfinavir (NFV): to be administered in two cycles (1250 mg BID (orally) for 7 days/cycle). Cycle #1 will conclude the day prior to SBRT. Cycle #2 will initiate the day after completion of SBRT.  
~ SBRT: to be administered in one day. However, if scheduling or safety prevents all lesions from being irradiated within one day, participants will complete Cycle #2 of Nelfinavir then undergo a minimum of 7 days “clear out”. Following this break participants will repeat Cycle #1 of Nelfinavir then receive radiation to the remaining lesions followed by a repeat Cycle #2 of Nelfinavir. This process may not exceed three “rounds” of treatment (NFV1, SBRT, NFV2) and may include repeat imaging and/or blood work. Accordingly, the study calendar will be affected.  
% Follow-up appointments will be scheduled based on date of SBRT completion.  
\* indicates optional  
@ +/- 30 days  
a. Including platelets.  
b. Albumin, Alkaline Phosphatase, Total Bilirubin, Bicarbonate, BUN, Calcium, Chloride, Creatinine, Glucose, Potassium, Total Protein, SGOT [AST], SPGT [ALT], Sodium.  
c. Tumor measurements are to be calculated after all radiographic tests.  
d. Will occur on the last day of Nelfinavir Cycle #1 or on date of SBRT administration and the last day of Nelfinavir Cycle #2. May be conducted via phone.  

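### Section 15.7 starts toxicity evaluability at SBRT, which conflicts with the 11.2 Safety Population; secondarily, no patient-level toxicity threshold is written for Cycle #2 or for starting a further round

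*Combined protocol and SAP*

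**What the plan says.** **Where toxicity counting starts.** Section 15.7 opens the period of toxicity evaluability at a patient's first SBRT treatment. Section 11.2 defines a Safety Population of enrolled subjects who took one or more doses of study medication, and assigns it the assessment of safety and tolerability. Section 12.2.1 counts an adverse event from the first dose of study treatment or from any protocol procedure. Footnote d of the Study Calendar (section 10) schedules adverse event checks in both drug cycles: "Will occur on the last day of Nelfinavir Cycle #1 or on date of SBRT administration and the last day of Nelfinavir Cycle #2". Section 15.6 summarizes adverse events by type and grade and names no population. Later visits depend on SBRT: "Follow-up appointments will be scheduled based on date of SBRT completion".

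**What stops treatment in one patient.** Section 6.6 is a single criterion: "Unacceptable adverse events grade IV or greater with an attribution of possibly related while on Nelfinavir before SBRT". Section 8 says: "There will be no dose modifications". Section 6.10 lists withdrawal reasons, and toxicity is not among them. If lesions cannot all be irradiated in one day, "participants will complete Cycle #2 of Nelfinavir then undergo a minimum of 7 days" of clear-out (6.4). Section 6.2 continues: "Following this break participants will repeat Cycle #1 of Nelfinavir then receive radiation to the remaining lesions followed by a repeat Cycle #2 of Nelfinavir". At most three rounds are allowed, and the process "may include repeat imaging and/or blood work". Section 7.3 adds a control at the pharmacy: "Nelfinavir will only be dispensed to the patient when the treating physician involved in the study provided a written order".

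**The concern.** Nelfinavir is taken alone for seven days before SBRT, so the choice of start date decides whether a whole drug cycle counts. Under 15.7, a patient whose drug toxicity prevents SBRT never becomes evaluable for toxicity. Those are the patients 6.6 removes, so the worst drug-only outcomes are the ones most likely to drop out of the summary. Their events should still reach the case report forms, but with no SBRT date the calendar gives them no follow-up visit.

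The second issue is that 6.6 ends where combined exposure begins, in a combination that 15.3 says is untried in this population. A related grade IV event in Cycle #1 has a written consequence. The same event in Cycle #2 has none for that patient, so re-treatment may differ between physicians.

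**Working it through.** **1. The start points side by side.**

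| Section | What it governs | Starts at |
|---|---|---|
| 11.2 | Safety Population | first nelfinavir dose |
| 12.2.1 | definition of an adverse event | first dose or any protocol procedure |
| 10, footnote d | scheduled checks | includes the end of Cycle #1 |
| 15.6 | adverse event summary | not stated |
| 15.7 | evaluability for toxicity | first SBRT |

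The conflict with 11.2 is direct, because both sections say who is assessed for safety. With 12.2.1 and footnote d it is a mismatch of time window: events are defined and collected in a period that 15.7 does not evaluate.

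**2. How much exposure 15.7 leaves out.** Dosing is twice daily for 7 days, so a cycle is 2 × 7 = 14 doses and a round is 2 × 14 = 28. Cycle #1 precedes SBRT, so 14 / 28 = 50% of one round's doses fall before evaluability starts. For a patient never irradiated, all doses taken fall outside.

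**3. Could this reach a stopping decision?** I first reproduced the plan's own rule. With the 15.4 prior Beta(0.5, 5.5), the posterior after x events in n patients is Beta(0.5 + x, 5.5 + n − x), and the rule stops when P(rate > 0.20) ≥ 0.75. The prior mean is 0.5 / 6 = 8.3%, and its 5th and 95th percentiles are 0.04% and 30.6%, as stated. The stopping table reproduces at every n from 7 to 42. The exact chance of declaring the regimen unsafe is 32.5% at a true rate of 0.20 (stated 32.7%) and 81.4% at 0.30 (stated 81.9%).

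The following examples hold only if 15.7 overrides 11.2. The two 15.4 examples also require that drug toxicity before irradiation counts under a rule 15.4 describes as site-specific. None of them is an expected frequency.

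- Run-in (15.3): 3 events in the first six suspends the study. If one of them was in a patient removed in Cycle #1 and is not counted, 2 remain and accrual proceeds.
- 15.4 boundary: 4 events in 8 patients gives Beta(4.5, 9.5) and P = 0.837, so stop. Leaving that patient out gives 3 in 7, Beta(3.5, 9.5) and P = 0.688, so continue.
- 15.4 overall: assume a share of grade 4/5 events arises before SBRT and goes uncounted, with the patients kept in the denominator. At a true rate of 0.30 the chance of stopping is 81% with none uncounted, and 69%, 46% or 12% with 10%, 25% or 50% uncounted. The shares are assumptions; the documents give none.

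**4. What 6.6 covers.**

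| Step | Patient-level threshold |
|---|---|
| First Cycle #1 | yes, 6.6 |
| Cycle #2, any round | none written |
| Decision to start another round | none written |
| Repeat Cycle #1 | unclear: before the next SBRT, but after the first |

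In one round, 14 of 28 doses lie outside 6.6. Three rounds are 6 × 14 = 84 doses. If 6.6 applies per round, 3 × 14 = 42 lie outside; if it means the first SBRT only, 84 − 14 = 70 do. Every Cycle #2 dose is outside on either reading. These are counts of scheduled doses, not of risk.

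**The case against.** **On 15.7.** The best reply is that the safety data are not lost. Section 11.2 already assigns safety to anyone with one dose, 15.6 adds no SBRT restriction, the calendar checks Cycle #1, and 12.1 and 12.7.1 require events to be recorded and followed with resolution and outcome. On that view 15.7 is one stray sentence. This stands as far as collection goes, so a reader who infers that Cycle #1 toxicity goes unrecorded, or that the summary is certain to be biased, goes beyond the documents. The bias is conditional on 15.7 being applied. But 15.7 sits in the statistical section under toxicity evaluation, and nothing ranks it below 11.2.

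**On 6.6.** Judgment has room to work. The clear-out has a minimum and no maximum, a written order is needed, checks fall at the end of each cycle, and barring dose modification does not forbid discontinuation. Sections 15.3 and 15.4 set thresholds that reach events after SBRT. All of this is right, and it makes the point secondary. What remains is that no grade is attached to the order or the checks, and that 15.3 and 15.4 act on the trial or its enrollment, not on one patient's next dose.

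**Stronger readings to avoid.** A reader might infer that nothing covers a repeat round. That is too broad, because a repeat Cycle #1 is again nelfinavir ahead of an SBRT session and 6.6 can be read to include it. A reader might also infer that stopping in Cycle #2 costs a patient a place in the 11.2 Evaluable Population. That definition counts 28 doses before SBRT, while one round gives only 14 before it, so stopping Cycle #2 does not create the shortfall.

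The text of Appendix II is not in the extract. Section 13 describes it as monitoring oversight, which gives no sign of a patient-level rule, but this cannot be confirmed.

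**Conclusion.** The main point holds: 15.7 is wrong as written because it conflicts with 11.2. If applied, it drops half the doses of a one-round course from toxicity evaluation, along with all patients never irradiated, and it understates toxicity. The number of such patients is not given, so no patient count is claimed. It is probably small, since 12.5 describes most nelfinavir adverse events as mild. The run-in and 15.4 examples show that one uncounted event could change a decision at a boundary, under the conditions stated with them.

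The 6.6 point holds in a narrower form, as a cheap safety improvement. No patient-level threshold is visible for Cycle #2 or for starting a further round, and coverage of a repeat Cycle #1 is ambiguous. It is reasonable that removal from the study is limited to the time before SBRT; what is missing is a rule for stopping or restarting the drug.

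Neither point changes the sample size, power or significance level.

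**What to change.** **Toxicity evaluation (main).**
- Change 15.7 so that patients are evaluable for toxicity from the first dose of nelfinavir.
- State that the 11.2 Safety Population governs the 15.6 adverse event summary.
- For patients who took nelfinavir but had no SBRT, add one telephone adverse event contact about 30 days after the last dose.

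**Patient-level rule (secondary).**
- In 6.6, state that a grade IV or greater event at least possibly related to nelfinavir, in any cycle of any round, stops further nelfinavir and bars a repeat round.
- Keep patients already irradiated in follow-up and in the 15.5 analysis population.
- Check the rule at the footnote d contact and again before the 7.3 written order.
- Whether to set a recovery level for grade 3 events before another round, and which, is for the investigator to choose.

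**Cost.** Amendment wording and a few telephone calls. The downside is that a few patients may have lesions left untreated on protocol.
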